site at Visit 5 Adverse events. Protocol compliance will be assessed by questioning the patient about their use of MED3000 and the number of unused tubes of MED3000 available. Patients will be asked about any changes to their concomitant medication and any new or changes to AEs (including their partner). Additionally, patients will be asked whether the patient or partner predominantly applied the gel to the glans penis prior to sexual intercourse.

Visit 4 (phone -Week 8 ( $\pm$  1 week)): Patients will be asked to complete the IIEF, EPIC, climacturia and SEAR questionnaires. The patient will bring the completed questionnaires to the site at Visit 5. Protocol compliance will be assessed by questioning the patient about their use of MED3000 and the number of unused tubes of MED3000 available. Patients will be asked about any changes to their concomitant medication and any new or changes to AEs (including their partner). Additionally, patients will be asked whether the patient or partner predominantly applied the gel to the glans penis prior to sexual intercourse.

Visit 5 (on-site -Week 12 ( $\pm$  1 week)): Patients have PSA serum samples taken and have a genital examination. Patients will also complete the IIEF, EPIC, climacturia and SEAR questionnaires. An assessment of the stretched flaccid penile length will be performed, heart rate and blood pressure will be measured. AEs, changes in concomitant treatment, and protocol compliance and a genital assessment will be assessed. The patient will return all used MED3000 tubes and unused MED3000 treatment at this visit and full verification of MED3000 usage compliance determined. The site will also perform an assessment of the patient's 24 hour pad weight and the number of pads used. Additionally, patients will be asked whether the patient or partner predominantly applied the gel to the glans penis prior to sexual intercourse.

Follow-up Visit 6 (phone-7 day post-study treatment, ( $\pm$  2 days)): Patients will provide details about ongoing or new adverse events and any new concomitant treatment. Usage of erectogenic aids will also be recorded. Patient will be instructed to continue with his primary urologist for PSA monitoring per standard of care.

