#### **Intervention**

Patients will be instructed to make at least 4 intercourse attempts in each of the three 4-weekly periods during treatment (Weeks 1-4, 5-8, 9-12). Patients will apply a single dose (approximately 300 mg) to the glans penis and rub in for at least 15 seconds (to ensure a thorough distribution of gel) prior to each sexual intercourse attempt. Patients may have telehealth visits at Weeks 4 (Visit 3), 8 (Visit 4) and the 13-week follow-up visit (Visit 6). The patient will be expected to attend the site for the Screening (Visit 1), Baseline (Visit 2), and 12 week (Visit 5) assessments. The patient reported outcome questionnaires (IIEF, SEAR, EPIC and climacturia) will be completed at Screening (Visit 1), Baseline (Visit 2), and the end of each of the 4-weekly periods (Weeks 4, 8, and 12). At study visits where it is not necessary for the patients to attend the site in person (Visits 3, 4, and 6), the questionnaires will be completed by the patients at home using paper copies of the respective questionnaires. Site staff will phone the patient to prompt them to complete the questionnaires and ask how many device assisted sexual intercourse attempts the patient had. The patients will be expected to bring the completed questionnaires and used and unused MED3000 tubes to site at their next on-site visit where a compliance assessment will be performed.

The site will encourage patient retention in the study by following up with the patients periodically between study visits if there are any questions or concerns from patients. Additionally,

the site will send reminders to the patients of upcoming on-site study visit.

On June 6, 2022 the Food and Drug Administration determined the proposed investigation is a nonsignificant risk (NSR) device study because it does not meet the definition of a significant risk (SR) device under 21 CFR 812.3 (m) of the investigational device exemptions (IDE) regulation (21 CFR 812).

Safety will be evaluated throughout the study, whilst patients are on treatment by evaluating all reported adverse events (AEs) and the use of concomitant treatments. Additionally, standard assessments including physical examinations and visual examination of the penis, vital signs (BP, heart rate [HR], body temperature) will be conducted at the screening and baseline visits (Visits 1 and 2), and Week 12 (Visit 5). Details relating to AEs and concomitant medication will be collected during the patient's study contact with the site.

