### ***Schedule of Assessments (Core Investigation)***

	Screening (5 or 4 weeks before Day 1) 	Treatment Period (12 Weeks)				Follow-up Visit
	Visit 1	Visit 2 (Day 1)	Visit 3  (Week 4 ± 1 week)	Visit 4  (Week 8 ± 1 week)	Visit 5  (Week 12 ±1 week)	Visit 6  (Week 13 ±1 week)
Eligibility assessment of male & female	X	X 				
Informed consent (male and female) 	X					
PSA Serum 	X					

Mass General Brigham Institutional Review Board  
Intervention/Interaction Detailed Protocol

	Screening (5 or 4 weeks before Day 1) 	Treatment Period (12 Weeks)			Follow-up Visit
Hormonal assays (testosterone) 	X				
Genital examination	X				X
BMI	X				
IIEF	X	X 	X	X	X
EPIC + climacturia	X	X	X	X	X
SEAR	X	X 	X	X	X
Heart rate and blood pressure	X	X			X
Penile length measurement	X				X
24 hour pad weight and number of pads used	X				X
Treatment		←	→		
MED3000 dispensing		X 			
Adverse events reporting (including device deficiencies) 		←	→		
Concomitant treatment	←				→

 Patients using ED treatment (device or medication), a 5-week screening period will be observed (including 1 week washout). Patients not using any form of ED treatment only need to observe a 4-week screening period.

 Assessments at this Visit may be performed via Telehealth. The site will phone the patients to prompt them to complete the IIEF, SEAR, EPIC and climacturia questionnaires, if required in the

protocol schedule of assessments. The completed questionnaires will be brought to the site at the next scheduled on-site visit.

 Eligibility assessment at Visit 2 will consider whether the patient has had the 4 requested sexual intercourse attempts during the screening period and has a score of <= 25 on the IIEF-EF questionnaire at Visit 2.

 IIEF, EPIC, climacturia, and SEAR Baseline scores will be obtained at Visit 2

 At Visit 2, sufficient MED3000 will be dispensed to meet the needs of each patient's entire participation in the study (36 tubes)

 Adverse Events will be recorded from the point that patient and partner sign their respective informed consent forms.

 Visit 5 assessments will be undertaken for patients who withdraw from the treatment period prematurely

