### **Adverse Events**

AEs will be monitored and assessed throughout a patient's involvement in the study (from the point of signing the ICF to the follow up visit (Visit 6). At each study visit, the site staff will ask the patient about any AEs the patient and their partner may have experienced. The site study staff will also ask the patient about any device deficiencies that they experienced.

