### **Withdrawal Criteria**

- Occurrence of a serious adverse event during the treatment period will result in termination of MED3000 topical gel treatment.
- A subject may be withdrawn from MED3000 topical gel treatment by the investigator, regardless of consent, if the investigator determines health and/or safety concerns preclude continuation of investigational product treatment. If a subjective is not sufficiently cooperative may be grounds for dismissal from trial participation.
- A subject may be withdrawn from the study by the investigator in the event that a late inclusion/exclusion criteria violation is found to have occurred and there are corresponding health and/or safety concerns.
- Tumor recurrence (defined as biochemical recurrence: serum PSA  $\geq 0.2$  ng/ml) during the MED3000 treatment period will result in immediate withdrawal from the study such that adjuvant/salvage therapies for cancer control will be needed.
- A subject may withdraw from the study at any time, for personal reasons or otherwise.

Information regarding the timing and type of withdrawal (treatment and/or study) will be documented. Information collected for study purposes may be maintained and used by investigators after study withdrawal has occurred, but no new information will be collected after that time. Subject withdrawal due to an AE will be distinguished from withdrawal due to other reasons by appropriate documentation.

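### The bar on new data after any study withdrawal removes the recorded post-treatment adverse event enquiry for men withdrawn by the investigator or by rule who still consent

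*Combined protocol and SAP*

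**What the plan says.** **AE period.** Section 6, Adverse Events, runs monitoring "from the point of signing the ICF to the follow up visit (Visit 6"). Staff ask the man about his partner's AEs as well as his own. Treatment-related AEs in both are the fourth secondary objective in Section 2, and the proportion of patients with such events is a listed endpoint in Section 9.

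**Withdrawal.** Section 10, Withdrawal Criteria, distinguishes leaving the gel from leaving the study. Two routes out of the study are not the man's choice. One is the investigator's: "A subject may be withdrawn from the study by the investigator in the event that a late inclusion/exclusion criteria violation" comes to light and carries a health or safety concern. The other is mandatory: biochemical recurrence during treatment. The section then says that data already held may be kept and used after study withdrawal, but "no new information will be collected after that time".

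**Early stopping of treatment.** Footnote 7 of the Schedule of Assessments says "Visit 5 assessments will be undertaken for patients who withdraw from the treatment period prematurely". It gives no date and does not mention Visit 6.

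**Timing of Visit 6.** Study Visits has "Follow-up Visit 6 (phone-7 day post-study treatment", with a tolerance of 2 days. The schedule header has "Visit 6 2 (Week 13 ±1 week"), after "Visit 5 7 (Week 12 ±1 week"). Section 3, Intervention, calls it "the 13-week follow-up visit (Visit 6"), and the stopping rules in Section 10 also place it at week 13. No text ranks the two rules.

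**The concern.** A sentence that stops data collection is the right consequence when a man withdraws consent. Here it applies to every study withdrawal, including those decided by the investigator or imposed by rule. One of these routes is defined by a safety concern, yet a man who takes it loses the recorded enquiry that completers get about a week after their last treatment. His partner's AEs are asked about through him, so that scheduled enquiry goes too.

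The plan is more protective elsewhere. If the whole study stops early, the stopping rules keep treated patients in follow-up to Visit 6 where possible.

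What is at stake is safety follow-up of individual couples and the completeness of AE capture. A lesser matter is that Visit 6, which closes the AE period, has two timing rules with different anchors and tolerances.

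**Working it through.** The plan states no figure on this point. The check is a reading of the withdrawal routes, followed by window arithmetic.

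**1. Which routes trigger the bar (Section 10, Withdrawal Criteria)**

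- Serious AE during treatment: ends the gel only. Not triggered. (Assessment of Safety says such an event may end treatment; Withdrawal Criteria says it will. Both concern treatment.)
- Investigator's general health or safety judgement: withdrawal from the gel. Not triggered.
- Late-found eligibility violation with a safety concern: withdrawal from the study. Triggered, although the man may still consent.
- Biochemical recurrence during treatment: mandatory withdrawal from the study. Triggered, although the man may still consent.
- The man's own decision to leave: triggered, and appropriate where it withdraws consent.

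The section also allows dismissal from the trial for poor cooperation. If that counts as study withdrawal the bar reaches it too, but it is not a safety route and nothing below depends on it.

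**2. What remains for a man in the two triggered groups**

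- Footnote 7 assessments can be done on the day of withdrawal.
- Serious AEs are followed to resolution or stabilization, and subjects have a telephone number for reporting AEs (Assessment of Safety).
- AEs still open at the last assessment are followed by the investigator, but outside the eCRF. The manufacturer may ask for more information on ongoing events (Section 6, text on the AE collection period).
- None of these schedules an enquiry about a new non-serious AE after withdrawal, and the bar prevents its being recorded.

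For a man whose gel stops on the day of withdrawal, planned post-treatment follow-up of 7 − 2 = 5 to 7 + 2 = 9 days becomes 0.

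**3. Visit 6 windows**

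Take week n as day 7n from Day 1, and the end of treatment as the day of Visit 5.

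- Visit 5 by the schedule: 84 ± 7 = days 77 to 91.
- Visit 6 by the schedule: 91 ± 7 = days 84 to 98.
- Visit 6 by the text, for Visit 5 on day v: v + 5 to v + 9.
- Days meeting both: max(v + 5, 84) to min(v + 9, 98).

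Results for completers:

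- v = 77: days 84 to 86, 3 days
- v = 78: days 84 to 87, 4 days
- v = 79 to 89: 5 days
- v = 90: days 95 to 98, 4 days
- v = 91: days 96 to 98, 3 days

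For a man formally taken off gel who stays in the study and has Visit 5 brought forward to day s, a common day needs s + 9 ≥ 84, that is s ≥ 75. For s ≤ 74 there is none; s = 28, for example, gives days 33 to 37 against 84 to 98. The documents do not say whether his remaining scheduled contacts continue. A man who simply stops using this on-demand gel and keeps his visits has no clash.

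**4. Effect on the AE proportion**

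Take 20 treated men (Section 9 says approximately 20). One man moves the proportion by at most 1/20 = 5 points, and only if his first treatment-related AE falls in the uncovered interval. The documents give no rates, so assume 0 to 2 such men and a 1 to 5% chance of such an event in each:

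- 0 men: 0 points
- 1 man at 1%: 1 × 0.01 × 5 = 0.05 points
- 2 men at 5%: 2 × 0.05 × 5 = 0.5 points

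For comparison, the exact 95% interval for 0 events in 20 has upper limit 1 − 0.025^(1/20) = 16.8%.

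**The case against.** The strongest reply is that almost nobody is affected. The main safety routes, a serious AE and the investigator's health or safety judgement, end the gel only, so those men are outside the bar. A reader might infer that every man withdrawn for safety loses his follow-up; the documents do not support that. The recurrence route is also narrow. It requires detection during treatment, while the schedule lists PSA only at screening, and the sample in the Visit 5 description is drawn when the gel is handed back. Section 1 reports no serious AEs in the earlier trial. All of this stands.

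A reader might also infer that the call itself is forbidden. The text bars collecting information, and Visit 6 also tells the man to continue PSA monitoring with his urologist. That stands too, though collecting information is nearly all the visit does.

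On timing, two stronger readings are tempting:

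- The schedule windows alone allow Visit 6 from 84 − 91 = −7 to 98 − 77 = +21 days relative to Visit 5. This requires ignoring the visit description, which places the call after treatment, and the schedule's own separate follow-up column.
- An early stopper could be said to lose weeks of AE follow-up. That requires his remaining contacts to be dropped, which no text says. If they are kept, nothing is lost.

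The existing safeguards are real, and a withdrawn man is not left without a way to report a problem. They do not, however, provide a scheduled and recorded enquiry about new events.

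**Conclusion.** The point holds as a minor one. The withdrawal wording does not separate withdrawal of consent from withdrawal decided by the investigator or required by rule. Two groups of men who may still consent therefore lose the recorded Visit 6 AE enquiry, for themselves and their partners: 5 to 9 days of planned follow-up become none.

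The number of men is unknown and probably very small. The expected shift of 0 to 0.5 points in the AE proportion rests on the assumed rates above and is negligible beside the trial's precision. The gain from a correction is in per-patient safety follow-up, not in the estimate. The primary IIEF-EF analysis is unaffected.

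The two Visit 6 rules are mainly a wording inconsistency. Completers can always satisfy both. Only a formal early stopper with Visit 5 moved to day 74 or earlier has no common date, and for him the plan is silent rather than wrong.

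**What to change.** **Main change (Section 10, Withdrawal Criteria).** Limit the bar on new information to men who withdraw consent. State that all other withdrawn men still have the footnote 7 assessments and a Visit 6 AE call covering both partners, recorded in the eCRF.

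**Secondary clarification (Section 3, Intervention; the schedule header; Study Visits; the stopping rules).** Define Visit 6 as 7 ± 2 days after the actual Visit 5 or early-termination visit, and never before it. Add that men who stop the gel but stay in the study keep their remaining AE contacts through week 13, with the AE period closing at the last of these.

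**Cost.** About one extra phone call per affected man; the other contacts are already scheduled. The change needs a protocol amendment with IRB approval, as Section 10, Deviations from the Protocol, requires. It may also need a check of what the consent form says about data collected after withdrawal; that form is not among the documents reviewed. No follow-up is given up, and the right to withdraw consent is unchanged.

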#### **End of Study Definition**

The study ends once the last patient enrolled in the study has undergone Visit 6 or lost to follow-up.

#### **Assessment of Safety**

Safety monitoring will be performed in the following manner: The investigator will routinely monitor each subject and their partner for the occurrence of AEs or any unusual medical occurrence. This will include a genital examination of the patient before and after MED3000

Mass General Brigham Institutional Review Board  
Intervention/Interaction Detailed Protocol

---

topical gel treatment, as well as interviews with each subject during each treatment visit and the Follow-up Visit. In addition, all subjects will be provided with a telephone number to call in case of medical emergencies, or to report AEs at any time.

The Principal Investigator will follow IRB policy that any Unanticipated Problem Involving Risks to Subjects or Others (UPIRTSO) or Unanticipated Adverse Device Effects (UADE) are reported to the IRB within 5 working days/7 calendar days of the date the investigator first becomes aware of the problem. Additionally, the PI will maintain an Adverse Event Log for the duration of the study.

A description of each AE will be recorded including the date of onset, time course, severity, relatedness to study treatment, action taken regarding the study treatment, outcome, and any treatment administered. The investigator will list the specific diagnosis, disease, or syndrome rather than associated signs and symptoms.

All serious adverse events ("SAEs") will be followed by the investigator until resolution or stabilization and reported to the IRB as per the local requirements. Any SAE that is related to MED3000 treatment, or is a not expected occurrence, will be reported within 24 hours of knowledge of the event to the device provider (Futura Medical Developments Limited).

Occurrence of an SAE during the treatment period may result in termination of study treatment.

A subject may be withdrawn by the investigator, regardless of consent, if the investigator determines health and/or safety concerns preclude continuation of investigational product treatment.

### **Adverse Events**

AEs will be monitored and assessed throughout a patient's involvement in the study (from the point of signing the ICF to the follow up visit (Visit 6). At each study visit, the site staff will ask the patient about any AEs the patient and their partner may have experienced. The site study staff will also ask the patient about any device deficiencies that they experienced.

### Adverse Event Grading Scheme

Mass General Brigham Institutional Review Board  
Intervention/Interaction Detailed Protocol

Causality/relationship and intensity of an AE to the device, or affected site will be determined by the investigator and will be classified as one of the following:

Unrelated	The event is clearly related to an event that may be due to environmental or accidental occurrence or other factors such as the subject's clinical state, therapeutic interventions, or concomitant drugs administered to the subject.
Possibly related	The event follows a reasonable temporal sequence from the time of drug administration or use of device, and/or follows a known response pattern to the study drug or device, but could have been produced by other factors such as the subject's clinical condition, therapeutic interventions, or concomitant drugs administered to the subject.
Probably related	The event follows a reasonable temporal sequence from the time of drug administration or use of device, and follows a known response pattern to the study drug or device, and cannot be reasonably explained by other factors such as the subject's clinical condition, therapeutic interventions, or concomitant drugs administered to the subject.
Related	The event follows a reasonable temporal sequence from the time of drug administration or use of device, and follows a known response pattern to the study drug or device, and cannot be reasonably explained by other factors such as the subject's clinical condition, therapeutic interventions, or concomitant drugs administered to the subject, and either occurs immediately following study drug administration or use of device or improves on stopping the study drug or device, or reappears on repeat exposure.

Severity: events will be classified as outlined in the below table, which reflects the Common Terminology for Adverse Events ("CTCAE") scale.

Grade	Description
1	Mild; asymptomatic or mild symptoms; clinical or diagnostic observations only; intervention not indicated.
2	Moderate; minimal, local or noninvasive intervention indicated; limiting age-appropriate instrumental ADL*.
3	Severe or medically significant but not immediately life-threatening; hospitalization or prolongation of hospitalization indicated; disabling; limiting self care ADL**.
4	Life-threatening consequences; urgent intervention indicated.
5	Death related to AE.

\*Instrumental ADL refer to preparing meals, shopping for groceries or clothes, using the telephone, managing money, etc.

\*\*Self-care ADL refer to bathing, dressing and undressing, feeding self, using the toilet, taking medications, and not bedridden.

A Serious Adverse Event ("SAE") is an AE that meets one or more of the following criteria:

- Fatal;
- Life threatening;
- Results in an unanticipated or prolonged hospitalization;
- Results in a significant and persistent disability/incapacity;
- Results in a congenital anomaly or birth defect.

### **Adverse Device Effect (ADE)**

An AE related to the use of the investigational medical device. This

definition includes:

- AEs resulting from insufficient or inadequate instructions for use, deployment, implantation, installation, or operation, or any malfunction of the investigational medical device (malfunction is the failure of an investigational medical device to perform in accordance with its intended purpose when used in accordance with this protocol)
- Any event resulting from use error or from intentional misuse of the investigational medical device (user error is user action or lack of user action while using the medical device that leads to a different result than that intended by the manufacturer or expected by the user)

